#### 7.2 Participant recruitment

We aim to recruit 1386 participants across our three participating sites (~460 at each site). Staff interested in taking part will simply need to follow the link which will invite them to complete the online study screening for eligibly questions to ascertain their eligibility for inclusion into the study. To motivate staff to participate in the study, especially those concerned about job security if problems with hand dermatitis are identified, we will emphasize the potential benefits of our questionnaire, and guarantee the confidentiality of participants' information received.

We have followed the HRA guidance on 'Proportionate approach to seeking consent' when devised the following e-consent method. Those screened as eligible for the entry into the study will be asked to complete an online e-consent form via the eCRF (REDCap) portal before completing the self-assessment skin surveillance screening questionnaire. Importantly, prospective participants will be free to access the study Redcap portal at a time of their

choosing during the recruitment period. Participants will not be able to access their questionnaire once completed.

In addition, with the participants' consent we will collect NHS email addresses of participants and their line manager, to enable notification of assessment outcome.

At the end of the e-consent participants will be required to tick a box to confirm that "I certify that all of my information in the document is correct. I understand that clicking 'submit' will electronically sign the form and that signing this form electronically is the equivalent of signing a physical document".

After completing and electronically signing the e-consent form (form 1), participants will be given the option to click on a hyperlink which takes them directly to the Part 2 (form 2) of the questionnaire.

Participants will then be assigned a unique participant identification number (PIN) when logging into the portal.

Based on our previous work (5, 13,19) we anticipate that the recruitment period will need run for up to nine months.

By taking part in this study, participants will be provided with a remote digital assessment of hand dermatitis based on the data they provide (i.e. hand photographs). Therefore, if this assessment indicates that they may have hand dermatitis then we will recommend that they self-refer for follow-up advice and support from either their local occupational health, GP or pharmacist. Conversely, where applicable, participants may also benefit by receiving confirmation that they do not have hand dermatitis.

At the end of the questionnaire, participants will have the option to enter a prize draw to win a gift voucher. In total, there will be twenty £50 shopping vouchers available to win. Winners will be chosen at random. To be eligible to win this prize, participants will need to have completed the questionnaire, provided their hand photographs and a valid NHS email details.

Since we are testing digital methods for skin surveillance, paper-based study documentation will not be included in this study.

#### 7.3 Schedule of assessments for each visit

Completion of the questionnaire and the taking and uploading or sending of hand photographs should take no longer than five minutes to complete and will comprise separate forms.

On form 2, all eligible participants will be given a self-assessment screening questionnaire consisting of demographic information (including rating of Fitzpatrick skin type based on two domains; 'genetic disposition' and 'reaction to sun exposure'), dermatitis-related symptoms, hand washing frequency, and a single self-assessment screening question: 'In your opinion do you have hand/wrist dermatitis/eczema)?' with answer options of yes/no or unsure. Those who answer 'yes', or 'unsure' will then be asked the question: (ii) 'where is your hand/wrist dermatitis or skin condition located?'. The participants will be given eight options

**NHS Foundation Trust** 

and will be asked to tick all those that apply. The options will be left (or right) hand palm; left (or right) hand back; left (or right) wrist (front or back); between the fingers; and other part of hand/wrist (e.g. side of hand), with a request to specify the site if this category is selected. Participants will also be asked whether they have been told by a doctor that they have skin dermatitis or eczema (if so, how long ago).

Once form 2 is complete, all participants (whether they consider that they have hand dermatitis or not) will be instructed on how to take photographs of their hands and wrists and upload the photographs on to form 3 of the REDCap portal within 3 days of completing the questionnaire. Ideally, all participants will complete the upload of their hand photographs (on form 3) immediately after completing the self-assessment screening questionnaire (form 2). At the time of the upload, they will be asked whether any new changes to skincare or treatments have been used between completing the questionnaire. They will be asked to take one photo each of the front and backs of their hands and wrists using a smartphone following the standardised protocol which was developed and evaluated as part of the SCIN trial (13). As outlined in Part 2 of participant questionnaire (Taking and submitting hand photographs), participants will have the option to contact (via email) their local principal investigator should they require practical 1-2-1 assistance with taking and uploading selfie hand photographs.

After participants have submitted their data on the REDCap portal, an automatic standard email will be sent to participants to confirm their recruitment into the study and to encourage them to continue to monitor their hand for skin problems and to seek follow-up advice from their local OH department, GP or pharmacy.

Hand photographs (form 3 only) will be accessible to the study nurse via the REDcap portal and the study nurse will assess the presence of dermatitis using the Validated Investigator Global Assessment for Atopic Dermatitis (vIGA-AD) tool (20). Within the portal, the study nurse will then assign and score the photographs to five categories as per IGA score (Category 1: 'Clear'; Category 2: 'Almost clear'; Category 3: 'Mild'; Category 4: 'Moderate'; Category 5: 'Severe') with the first indicating 'absence of dermatitis' and any of the categories 2-5 indicating 'presence of dermatitis'. The dermatology nurse will also keep a separate category for the photographs for which they are unsure and another category for photographs which are insufficiently clear for assessment and which participants will be invited by the research team to resubmit new hand photographs. For the unsure cases, the photographs will be assessed by the dermatologist via the REDcap portal (form 3 only). Information on whether participants' hand photographs require further assessment by the study dermatologist (i.e. categorised as 'Unsure' by the study nurse) will also be recorded in REDcap, as it is relevant for future application of surveillance method.

Participants who provide photographs that are not sufficiently clear for assessment will be recontacted by a member of the central study team (not the study dermatologists or dermatology nurse) and invited on one occasion only to provide an additional set of hand photographs. In order to ensure that the photograph is taken within 3 days of the time as they are being assessed for presence of hand dermatitis, we will require them to re-answer the question *'In your opinion do you have hand/wrist dermatitis/eczema)?'* with answer options of *yes/no or unsure*. Those who answer 'yes', or 'unsure' will then be asked the question:

'*where is your hand/wrist dermatitis or skin condition located?*'. A separate form (form 6) will be used to collect re-submitted hand photographs. Photographs that the dermatology nurse deems to be of too poor quality to assess will not be included in the final analysis.

Prior to assessing the presence of dermatitis, to ensure appropriate use of the vIGA-AD tool, the dermatologist nurse will be required to complete a training consisting of a video on best practices for using the scale to rate the severity of the disease and subsequently complete a certification examination as described by Simpson et al. (20)

Once the study nurse is fully trained, they will independently assess all hand photographs. After nurse's assessment has been completed, the presence or absence of dermatitis (vIGA score Categories 2-5 and Category 1, respectively) will be compared with participants' self-responses.

Photographs on discordant pairs (outcomes 2 and 3 described below) will be further assessed by the two study dermatologists who will assess presence of dermatitis. The dermatologist will independently assess the hand photographs for presence of hand dermatitis and score 1-5 on the vIGA scale. If the dermatologists' scores differ they will agree a score by discussion. The original nurse's assessment using the vIGA tool will be corrected for the dermatologists' expert opinion where needed.

The nurse's assessment of the hand photographs and any back up required by the study dermatologist with correction of the assessment on the vIGA scale where needed, will be considered the gold standard against which the questionnaire-based self-assessed presence of dermatitis (new proposed screening tool) will be compared. We will assess the acceptability of the self-assessment screening tool by incorporating several short questions into the study questionnaires.

The questionnaire we will also include several questions to capture participants views on the study material, and the instructions they have to follow to complete the self-assessment screening questionnaire and for taking and submitting hand photographs. Response options will be set out in Likert scale format to aid analyses of results. We will further ask their willingness to involve their line-managers in the skin surveillance. The questionnaire will also include the option for participants to provide further qualitative (free text) feedback on a) concerns about completing the questionnaires and/or uploading photos, b) on obstacles and facilitators to implementation of the proposed methods, and c) anything not covered by the questions above.

In addition to the staff questionnaire, we will administer a case report form to capture feedback from the clinical leads and service managers from the participating departments on the acceptability and feasibility of delivering the skin surveillance method in the clinical setting. We will also enquire about barriers/facilitators of implementing the proposed surveillance method and future practical strategies to optimise its use if this skin health surveillance activity was delegated to them. We will also enquire about existing skin surveillance approaches (if any) at each participating site. This data will be collected electronically using separate REDCap database under GSTT licence or Microsoft Forms and no personal identifiable data will be collected.

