## **12 STATISTICAL CONSIDERATIONS**

The following outlines the proposed statistical analyses methods planned as they relate to each research question (RQ).

• RQ1 Can a self-assessed hand dermatitis screening questionnaire for at-risk health care workers reliably be used as part of a health surveillance programme?

As the primary study outcome, we will calculate the sensitivity of the proposed selfassessment screening tool (single-item self-reported dermatitis) along with its 95% confidence intervals when compared with the gold standard (nurse's dermatitis assessment from the hand photographs). We will further assess its specificity, positive and negative predictive value. The analysis will be conducted for all participants and then separately by medium and high risk of hand dermatitis, determined by frequency of hand washing 10-20 times per day (medium risk), and more than 20 times per day (high risk).

• RQ2 What is the sensitivity and specificity of the hand dermatitis self-assessment screening questionnaire in identifying early hand dermatitis, and is it similar across all Fitzpatrick skin phototypes and occupational (clinical vs non-clinical) groups?

The accuracy of hand dermatitis self-assessment screening questionnaire will further be explored in sub- groups of our sample participants. Primarily sensitivity, and specificity, and further positive and negative predictive values, as indicators of the accuracy of the screening test will be estimated for clinical and non-clinical staff and their differences will be compared statistically. Due to the high number of NHS staff of non-white ethnic origin, and the lack of information about hand dermatitis or ability to self-report its presence across the six Fitzpatrick skin phototypes, we will also stratify our results by Fitzpatrick phototypes, with a potential to identify skin phototypes in which accuracy of the screening questionnaire is lower.

• RQ3 Is the self-assessment screening questionnaire and photographic method acceptable and feasible to use in healthcare staff in a busy NHS setting?

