We will assess this by asking a series of questions relating to the ease with which participants are able to a) complete the self-assessment screening questionnaire and b) follow the instructions for taking and submitting hand photographs. We will set out the response options in Likert scale format to aid analyses of results. We will further ask their willingness to involve their line-managers in the skin surveillance and whether they would accept referral to occupational health if the assessment showed signs of dermatitis. The questionnaire will also include the option for participants to provide further qualitative (free text) feedback on a) reservations about completing the questionnaires and/or uploading photos, b) on barriers and facilitators to implementation of the proposed methods, and c) anything not covered by the questions above. In addition, we will administer a brief case report form to capture feedback from the clinical leads and service managers from the participating departments on the acceptability and feasibility of delivering the skin surveillance method in the clinical setting. We will also enquire about barriers/facilitators of implementing the proposed surveillance method and future practical strategies to optimise its use if this skin health surveillance activity was delegated to them. We will also enquire about existing skin surveillance approaches (if any) at each participating site.

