#### 12.1 Statistical power

Considering as the primary study outcome the sensitivity of the single-item questionnaire (with secondary outcomes being its specificity, positive and negative predictive value) we enquired six occupational physicians with experience in NHS work what they would consider as the minimum acceptable sensitivity for such a self-assessment screening tool (single-item questionnaire) to be administered by managers to detect hand dermatitis in at risk healthcare workers. The majority (3 out of 4 who responded to our enquiry) reported a sensitivity of 80%. Assuming a prevalence of hand dermatitis among healthcare workers of 15%, and a high sensitivity of 0.90% with a width of confidence interval 0.10 (targeting a lower bound for sensitivity of 0.80), the estimated required sample size is 231. We hypothesised the same prevalence for clinical and non-clinical staff, and also for staff of light, medium and dark skin. This totals 1386 participants (i.e. 231 participants for each of the 6 groups clinical/non-clinical staff and type of skin), which would give sufficient power for any analysis stratification. We aim to recruit approximately equal numbers (~460 participants) from each of the 3 sites in the study.

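### The 1386 target leaves no room for participants without an assessable photograph, so cell-level precision falls short, and accuracy is biased if photograph return depends on the questionnaire answer

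*Protocol*

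**What the plan says.** The screening question is answered on form 2. Photographs follow on form 3, within 3 days. Section 7.3 prefers no gap ("Ideally, all participants will complete the upload of their hand photographs (on form 3) immediately after completing the self-assessment screening questionnaire") but does not require this. A participant whose photographs are unclear is invited once to send another set. After that the rule is: "Photographs that the dermatology nurse deems to be of too poor quality to assess will not be included in the final analysis".

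Section 12 makes sensitivity the primary outcome, "along with its 95% confidence intervals when compared with the gold standard", which is the nurse's photograph assessment. Specificity and the predictive values follow.

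Section 12.1 gives the sample size. The inputs are "Assuming a prevalence of hand dermatitis among healthcare workers of 15" per cent and "a high sensitivity of 0.90% with a width of confidence interval 0.10 (targeting a lower bound for sensitivity of 0.80". From these, "the estimated required sample size is 231". That number is multiplied by six (clinical or non-clinical staff, by light, medium or dark skin), and the section concludes that power is adequate for whatever stratification is run. Section 7.2 uses the same total for enrolment: "We aim to recruit 1386 participants across our three participating sites".

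For feasibility and acceptability (RQ3), section 12 says: "We will assess this by asking a series of questions relating to the ease with which participants are able to" complete the questionnaire and follow the photograph instructions. Free text and feedback from clinical leads and managers are added.

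**The concern.** A participant counts towards sensitivity or specificity only with both an answer and an assessable photograph. The protocol expects some photographs to fail and excludes them, but its calculation treats everyone recruited as analysable. If each cell is sized with nothing to spare, any loss breaks the precision that the section promises for it.

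The second issue is selection. The answer is given before the photograph is sent, so whether an assessable photograph arrives may depend on the answer. If it does, the complete-case 2x2 table over- or under-represents questionnaire positives, and both sensitivity and specificity shift. Section 12.1 reports 80% as the minimum sensitivity named by most of the occupational physicians who replied, so a shift of a few points around that value could change the conclusion about the tool.

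**Working it through.** **Inputs from the protocol (sections 12 and 12.1).** 95% confidence (z = 1.96), prevalence 0.15, expected sensitivity 0.90 (printed with a stray per cent sign), target lower bound 0.80. The figure of 0.10 is called a width, but with a lower bound of 0.80 it must be the half-width. Read as the full width it would need 922 per group, not 231.

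**Reproducing the plan's figure.**
- Cases needed = 1.96² × 0.90 × 0.10 / 0.10² = 34.57.
- Participants needed = 34.57 / 0.15 = 230.5, rounded up to 231.
- Total = 6 × 231 = 1386.

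The figure reproduces exactly with no term for loss. The only slack is the rounding: 231 × 0.15 = 34.65 cases against 34.57 needed.

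**Precision per cell after loss.** The protocol gives no loss rate, so these are assumptions. People left = 231 × (1 − loss); cases = people × 0.15; half-width = 1.96 × √(0.09 / cases).

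| Assumed loss | People per cell | Cases | Half-width | Lower bound |
|---|---|---|---|---|
| 5% | 219.4 | 32.9 | 0.1025 | 0.7975 |
| 10% | 207.9 | 31.2 | 0.105 | 0.795 |
| 20% | 184.8 | 27.7 | 0.112 | 0.788 |
| 30% | 161.7 | 24.3 | 0.119 | 0.781 |

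**Precision at coarser levels.**
- Overall: 1386 × 0.90 × 0.15 = 187.1 cases at 10% loss, half-width 0.043. At 30% loss it is 0.049.
- Staff group, two equal halves at 20% loss: 1386 × 0.80 / 2 = 554 people, 83.2 cases, half-width about 0.065.
- Skin group, three equal thirds at 20% loss: 1386 × 0.80 / 3 = 370 people, 55.4 cases, half-width about 0.079.
- Six Fitzpatrick phototypes, if equal: 1386 / 6 = 231 before loss, so the cell table above applies again.

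**Bias from unequal return.** Let r₊ and r₋ be the proportions returning an assessable photograph after a positive and a negative answer, with return depending only on the answer.
- Observed sensitivity = Se·r₊ / (Se·r₊ + (1 − Se)·r₋)
- Observed specificity = Sp·r₋ / (Sp·r₋ + (1 − Sp)·r₊)

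With true sensitivity 0.80 and specificity 0.90 (all values assumed):

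| r₊ | r₋ | Observed sensitivity | Observed specificity |
|---|---|---|---|
| 0.90 | 0.90 | 0.800 | 0.900 |
| 0.90 | 0.80 | 0.818 | 0.889 |
| 0.90 | 0.70 | 0.837 | 0.875 |
| 0.70 | 0.90 | 0.757 | 0.920 |

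Third row in full: 0.80 × 0.90 / (0.80 × 0.90 + 0.20 × 0.70) = 0.72 / 0.86 = 0.837. At the same return rates a true sensitivity of 0.76 appears as 0.684 / (0.684 + 0.168) = 0.80. The predictive values condition on the answer, so this mechanism leaves them unchanged.

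**The case against.** Four points have weight.

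- **The stated exclusion is narrow.** Only photographs still unassessable after resubmission are expressly excluded. A reader might infer that the protocol also rules out participants who never upload. It does not say so; that follows only because accuracy is judged against the photograph, and a separate analysis plan could handle their missing reference result. Section 7.3 also confirms recruitment by email after data are submitted, so if recruited means photographs sent, non-uploaders fall outside the 1386. Unassessable photographs would still count within it.
- **Direction is open.** A reader might infer that sensitivity is inflated, because people who suspect dermatitis have more reason to upload. The documents do not support one direction. Section 7.2 mentions staff worried about job security if dermatitis is found, which could discourage positives. The same section offers a prize draw that requires photographs whatever the answer, and confirmation to those found clear. One-to-one help and submission by email also reduce loss.
- **The primary estimate is not in trouble.** A reader might infer that the study as a whole is too small. Overall precision stays near 0.05 or better up to 30% loss, and the coarser strata stay inside 0.10 if roughly equal. Convenience sampling may unbalance the cells more than a 10% loss would.
- **RQ3 is not judged only by those who succeed.** Section 11.1 places views on study processes in Part 2 as well. Free text covers concerns about uploading, managers give feedback, and nurse-unsure cases are recorded.

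These points limit the concern but do not remove it. Section 12.1 multiplies by six in order to support stratification, and at that level it leaves no margin.

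**Conclusion.** The point holds in a limited form. The calculation reproduces exactly without a loss term, and the same 1386 is the enrolment target, although the protocol foresees and excludes failed photographs. At cell level the 0.80 bound is missed at every loss rate examined, by a small amount: 0.795 at 10% and 0.788 at 20%. The general assurance about stratification is therefore not met for the cells it was built on. It is not undermined for the overall estimate, nor for two staff groups or three skin groups of similar size.

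Complete-case sensitivity and specificity are biased only if return of an assessable photograph differs by answer. On assumed rates the shift in sensitivity is about 2 points for a 10-point gap and 4 points for a 20-point gap, in either direction. That is modest, but enough to matter near 0.80. It rests on return rates the protocol does not give and on return depending only on the answer.

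**What to change.** 1. **Define the count.** In sections 7.2 and 12.1, say whether 1386 means participants recruited or participants with an assessable photograph. If recruited, restate per-cell precision over a range of losses, such as the 5% to 30% tabulated above, and limit the stratification claim to the levels where it holds. This costs a paragraph. Restoring 231 per cell by enrolment would take 231 / 0.90 = 257 per cell, 1542 in total, at 10% loss. Restating precision is preferable, because convenience sampling would not guarantee that the extra participants fill the short cells.
2. **Add a corrected estimate.** Beside the complete-case result, show sensitivity and specificity corrected for partial verification, by Begg-Greenes or by inverse-probability weights built from form 2 (answer, symptoms, skin group, occupation). Form 2 data exist for everyone who completed it. The cost is a missing-at-random assumption and a slightly wider interval.
3. **Report photograph flow under RQ3.** To the planned ratings and feedback, add the proportions uploaded, assessable at first attempt, assessable after resubmission, and nurse-unsure. Use all who completed form 2 as denominator, and split by questionnaire answer and skin group. This needs only tabulation of data held in REDCap, and it would show whether return does differ by answer.
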